9.5. Pharmacokinetics

9.5.1. Blood sample collection

• Blood samples for PK and metabolism analysis of GSK2838232 will be collected at the time points indicated in Schedule of Assessments (Table 2 and Table 3). The actual date and time of each blood sample collection will be recorded. The timing of PK samples may be altered and/or PK samples may be obtained at additional time points to ensure thorough PK monitoring. This will not require an amendment to the protocol.

Details of PK blood sample collection (including volume to be collected), processing, storage and shipping procedures are provided in the SRM.

9.5.2. Sample analysis

Concentrations of GSK2838232 will be determined in plasma using the currently approved bioanalytical methodology. Raw data will be archived in the GLP Archives, GSK.

• Once the plasma has been analyzed for GSK2838232, any remaining sample may be analyzed for other compound-related metabolites and the results reported under a separate PTS-DMPK, GlaxoSmithKline protocol.

9.6. Pharmacodynamics

Not applicable.

9.7. Genetics

Not applicable.

9.8. Biomarkers

Not applicable.

9.9. Health Economics OR Medical Resource Utilization and Health Economics

Not applicable.

9.10. DATA MANAGEMENT

- For this study participant data will be entered into ClinBase, transmitted electronically to GSK or designee and combined with data provided from other sources in a validated data system.
- Management of clinical data will be performed in accordance with applicable GSK standards and data cleaning procedures to ensure the integrity of the data, e.g., removing errors and inconsistencies in the data.
- Adverse events and concomitant medications terms will be coded using MedDRA (Medical Dictionary for Regulatory Activities) and an internal validated medication dictionary, GSKDrug.
- CRFs (including queries and audit trails) will be retained by PAREXEL, and a copy of the annotated CRF will be sent to GSK. Participant initials will not be collected or transmitted to GSK according to GSK policy.

10. STATISTICAL CONSIDERATIONS

All statistical analyses will be performed by PAREXEL International Early Phase Biostatistics. All statistical analyses will be performed using the latest available version of SAS (SAS Institute Inc., Cary, North Carolina, United States of America [USA]), version 9.3 or higher. PK parameters will be calculated using Phoenix WinNonlin (Certara, L.P., [name]), version 6.3 or higher.

Complete details will be documented in the Reporting and Analysis Plan (RAP).

Any deviations from the planned analyses will be described in the clinical study report.

10.1. Sample Size Determination

Sample sizes are based on prior relative bioavailability studies with GSK2838232 and take into account variability and logistical factors while no formal calculation of power or sample size for Parts 1 or 2 of the study was performed. A sample size of approximately 16 participants for Part 1 and 10 participants for Part 2, considering a drop-out rate of 25%, of the study should be sufficient to provide useful estimates of inter-participant variability for GSK2838232 PK parameters and safety assessments.

Additional participants will be randomized and enrolled to ensure a minimum of 12 evaluable participants for Part 1 (crossover of tablet and capsule) and 8 evaluable participants for Part 2 (6 active: 2 placebo).

Sample size assumptions

For Part 1 of the study: The between-subject variability (%CVb) for AUC(0- ∞), and Cmax parameters from previous studies at different doses were 21% to 47% and 41% to 44%, respectively. Assuming within-subject variability (%CVw) for AUC(0- ∞) and Cmax is 80% of highest between-subject variability (which will be 38% and 35%, respectively), and with the sample size of 12, it is estimated that the precision (i.e., half

width of the 90% confidence interval on the log scale) for the relative bioavailability assessment will be within 31.7% of the point estimate for AUC($0-\infty$), and within 29.0% of the point estimate for Cmax. If the point estimate of the ratio of geometric mean for Cmax is 1, then 90% confidence interval will be approximately (0.78, 1.29).

10.2. Populations for Analyses

For purposes of analysis, the following populations are defined:

All Participants Screened Population

The All Participants Screened Population will include all participants who consent to participate in the clinical study. Participants in this population will be used for disposition summary.

Safety Population

The Safety Population will include all participants who received at least 1 dose of the study treatment (including placebo) with at least 1 post-baseline safety assessment. Participants in this population will be used for all demographic and safety summaries or listings. The population will be defined separately for Part 1A, Part 1B and Part 2 of the study.

Pharmacokinetic Population

The PK Population will include all participants in the Safety population for whom at least one evaluable PK sample is obtained and analyzed. Pharmacokinetic samples that may be affected by protocol deviations will be reviewed by the study team to determine whether or not the sample will be excluded. All PK analyses will be based on this analysis population. The population will be defined separately for Part 1A, Part 1B, and Part 2 of the study.

10.3. Definition of Baseline

Unless specified, baseline will be the last value before the first dose of study treatment.

10.4. Statistical Analyses

All safety analyses will be performed on the Safety Population.

All PK analyses will be performed on the PK Population.

For assessment of relative bioavailability of tablet versus capsule (AUC($0-\infty$) and Cmax) and effect of food (AUC($0-\infty$), Cmax, and tmax), loge-transformed selected PK parameters (except tmax) will be analyzed using a mixed effects model. The point estimates and their associated 90% confidence interval (CI) will be provided for the

ratios, test/reference (for bioavailability) and fed/fasted (food effect) in PK parameter values on the original scale.

For the parameter tmax, the corresponding non-parametric analysis will be performed on the original scale using CIs for the estimation of the treatment difference.

Steady-state GSK2838232 concentrations will be assessed by estimating the slope of predose concentrations following repeated daily administration. Accumulation of plasma GSK2838232 will be assessed as the ratios of Day 11/Day 1 AUC(0- τ), Cmax, and C τ values.

10.4.1. Safety Analyses

Clinical safety observations will include AEs, vital sign measurements, ECGs and clinical laboratory measurements (hematology, clinical chemistry and urinalysis). Safety data will be tabulated and, where appropriate, analyzed by the use of descriptive statistics.

The number (%) of participants withdrawing from the study treatment, study and reason for withdrawal will be summarized for each treatment with placebo participants combined within each study part.

Reported AEs will be coded using Medical Dictionary for Regulatory Activities (MedDRA). The number (%) of participants with treatment-emergent AEs (TEAEs) and treatment-related AEs will be tabulated by system organ class (SOC), preferred term and by treatment group within each study part. Severity of the TEAEs and treatment-related AEs will also be summarized by SOC, preferred term and by treatment group within each study part. Deaths, SAEs and AEs leading to withdrawal will be listed.

Descriptive statistics for observed and change from baseline in laboratory parameters (if applicable), vital signs measurements and ECGs will be presented by treatment group within each study part. Clinical laboratory toxicities will be graded based on the Division of AIDS (DAIDS) grading system, as specified in Section 12.4, Appendix 4. Summaries of laboratory toxicity grade will be provided.

10.4.2. Pharmacokinetic Analyses

The following plasma PK parameters will be determined using standard non-compartmental methods as data permit and in compliance with the GlaxoSmithKline SOP:

Part 1:

- AUC(0-t)
- $AUC(0-\infty)$
- Cmax
- C24

- tlag
- tmax
- $t^{1/2}$
- tlast

Part 2:

Day 1 dose:

- AUC(0-τ)
- Cmax
- Cτ
- tmax
- tlag

Day 11 dose:

- AUC(0- τ)
- $AUC(0-\infty)$
- Cmax
- Cτ
- tmax
- t½
- tlast

Accumulation:

- $R(AUC(0-\tau))$
- R(Cmax)
- R(Cτ)

Any additional PK parameters that are calculated will be provided in the RAP. Actual elapsed times from dosing will be used in the PK analysis. The AUC will be determined using the linear-up/log-down trapezoidal rule. Individual PK parameter values will be listed, and a descriptive summary by treatment will be provided.

Pharmacokinetic data will be presented in graphical and/or tabular form and will be summarized descriptively. Plasma GSK2838232 concentration-time data will be listed by participant, treatment group and time and summarized by treatment group and time for each part of the study. Individual participant profiles for GSK2838232 concentration-time data will be presented on both a linear and semi-log scale. Linear and semi-log figures for mean and median GSK2838232 plasma concentrations versus time will also be generated.

10.4.2.1. Relative Bioavailability

In Part 1A, the following plasma PK parameters will be assessed to determine the relative bioavailability as data permit:

- AUC($0-\infty$)
- Cmax

The dependent variable will be the log-transformed PK parameters of interest ($AUC(0-\infty)$ and Cmax) and the independent variables will include a fixed effect for treatment (table or capsule), sequence and period, and participant as a random effect. The estimated difference and CI obtained on the log scale will be exponentiated to provide an estimate of the table to capsule ratio and its associated 90% CI.

10.4.2.2. Food Effect

Food effect will be assessed in Part 1 using Analysis of Variance (ANOVA). The dependent variable will be the log-transformed PK parameters of interest (AUC(0-∞) and Cmax) and the independent variables will include a fixed effect for treatment (with or without food) and subject as a random effect. The estimated difference and confidence interval (CI) obtained on the log scale will be exponentiated to provide an estimate of the fed to fasted ratio and its associated 90% CI.

10.4.2.3. Steady State Assessments

For Part 2, mean plasma GSK2838232 pre-dose values between Days 2 through 11 and $C\tau$ of Day 11 will be plotted against time. Achievement of plasma GSK2838232 steady-state will be assessed by calculating the 90% CI of the slope of the linear regression of log $(C\tau)$ versus time. The dependent variable in the linear regression model will be log $(C\tau)$ and the model will include a random intercept effect for participant and a fixed slope effect for study day. Steady state will be reached if the 90% CI for the slope estimate includes zero.

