9.2.5 Statistical Analyses / Methods

Details of the planned displays are provided in Appendix 12: List of Data Displays and will be based on GSK Data Standards and statistical principles.

Unless otherwise specified, endpoints / variables defined in Section 9.2.1 will be summarised using descriptive statistics, graphically presented (where appropriate) and listed.

Statistical Methodology Specification

Part 2 Steady State Assessments

Endpoint / Variables

GSK2838232 pre-dose values between Days 2 through 11

Model Specification

• Achievement of plasma GSK2838232 steady-state will be assessed by calculating the 90% CI of the slope of the linear regression of $\log_e(C\tau)$ versus time. The dependent variable in the mixed effect model will be $\log_e(C\tau)$ and the model will include a random intercept effect for participant and a fixed slope effect for study day. Day will be treated as a continuous variable in the model.

Model Checking & Diagnostics

- Model assumptions will be applied, but appropriate adjustments may be made based on the data.
- The Kenward and Roger method for approximating the denominator degrees of freedom and correcting for bias in the estimated variance-covariance of the fixed effects will be used.
- An unstructured covariance structure for the R matrix will be used by specifying 'type=UN' on the REPEATED line.
- In the event that this model fails to converge, alternative correlation structures may be considered such as CSH or CS.
- Akaike's Information Criteria (AIC) will be used to assist with the selection of covariance structure.
- Normality assumptions underlying the model used for analysis will be examined by obtaining a
 normal probability plot of the residuals and a plot of the residuals versus the fitted values (i.e.
 checking the normality assumption and constant variance assumption of the model
 respectively) to gain confidence that the model assumptions are reasonable.
- If there are any departures from the distributional assumptions, alternative models will be explored using appropriate transformed data.

Model Results Presentation

- Steady state will be reached if the pre-dose concentration slope estimate is close to zero or the 90% CI for the slope estimate includes zero.
- Mean plasma GSK2838232 pre-dose values between Days 2 through 11 and C_{τ} of Day 11 will be plotted against time on linear and semi-logarithmic scale..

Subgroup Analyses

Not applicable

Sensitivity and Supportive Analyses

Not applicable

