All the derived parameters described above will be listed. For each of these parameters, except tmax and tlag, the following summary statistics will be calculated for each treatment group: N, n, arithmetic mean, standard deviation (SD), median, minimum, maximum, geometric mean with associated 95% CI, standard deviation of logarithmically transformed data, and the between-participant CV (%CVb) based on the geometric mean for the loge-transformed PK parameters. For tmax and tlag, N, n,median, maximum, minimum, arithmetic mean and standard deviation will be calculated.

As per final RAP Section 9.2.5, statistical methodology section of Part 2 Steady State Assessment, end point or variable is given as GSK2838232 pre-dose values between Days 2 through 11, however it should be GSK2838232 pre-dose values between Days 3 through 11.

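### Part 2 declares steady state when the trough slope is merely non-significant, with no limit on the remaining rise, so time to steady state may be set a day or two early

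*Protocol*

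**What the plan says.** Time to steady state is a secondary objective of Part 2 (Protocol section 4, SAP 2.2). Log trough is regressed on day: "the model will include a random intercept effect for participant and a fixed slope effect for study day". The decision rule in Protocol 10.4.2.3, repeated in SAP 2.4, is "Steady state will be reached if the 90% CI for the slope estimate includes zero". SAP 9.2.5 widens it, so that it is enough if the "slope estimate is close to zero or the 90% CI for the slope estimate includes zero"; no number is attached to the first alternative.

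The Protocol plans to use the "mean plasma GSK2838232 pre-dose values between Days 2 through 11". The SAP Addendum, section 2.9, changes only the window: "however it should be GSK2838232 pre-dose values between Days 3 through 11". The decision rule stays as it was.

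Protocol 10.1 asks for "8 evaluable participants for Part 2 (6 active: 2 placebo"), and states that no formal power or sample size calculation was done. SAP 2.4 calls the analyses descriptive and exploratory. The mock shell for Table 5.18 (SAP 14.13, Non-Standard4) gives the slope and 90% CI for successive windows: Days 3-11, 4-11, 5-11 and 6-11.

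**The concern.** A two-sided 90% CI that includes zero means that a zero slope is not rejected at the 10% level. The rule turns this absence of evidence into a positive finding. It sets no bound on how much the troughs could still be rising. A wide interval passes because it is wide, so the rule rewards variability.

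What is at stake is the time itself. The documents do not say in words how the windows give a time. The natural reading of the shell is the earliest start day whose window passes. If a window that starts before plateau passes too readily, the reported time is too early.

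**Working it through.** **Inputs**

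- Participants contributing troughs: 6 active (Protocol 10.1).
- Window: Days 3-11, 9 troughs each (SAP Addendum 2.9).
- Half-life without ritonavir: 15 to 18 h (Protocol 3.2.1).
- Residual SD of log trough: not stated anywhere, so a range is shown. The value 0.16 is what a half-width of 0.014 in the mock shell (20 mg + RTV row, Days 3-11) implies if n = 6: 0.014 / 1.678 × √360 = 0.158. The value 0.25 is an intermediate assumption. The value 0.35 borrows the within-subject CV assumed for Part 1 AUC and Cmax, which "is 80% of highest between-subject variability (which will be 38% and 35%, respectively").

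**The plan's own figure.** The only Part 2 size figure is 10 enrolled for 8 evaluable, and 8 × 1.25 = 10. No error rate is stated for the steady-state rule, so there is none to reproduce.

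**Step 1: how far below plateau the troughs are.** With once-daily dosing and one-compartment kinetics, the pre-dose trough on Day d as a share of plateau is 1 − 2^(−24(d−1)/t½).

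| t½ | Day 3 | Day 4 | Day 5 | Day 11 |
|---|---|---|---|---|
| 15 h | 89% | 96% | 99% | 100% |
| 18 h | 84% | 94% | 98% | 99.99% |

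**Step 2: precision of the slope.** For days 3 to 11 the sum of squared deviations is 60, so SE = SD / √(6 × 60), with df = 6 × 8 − 1 = 47 and t = 1.678. The least-squares slope of the true log trough is 0.010 per day at 15 h and 0.016 at 18 h.

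**Step 3: the rise that a passing interval can still contain.** The half-width is 1.678 × SD / √360, which is 0.0142 at SD 0.16 and 0.0221 at SD 0.25. An interval that just touches zero from above has an upper limit of twice that. Over 8 days this is exp(2 × 0.0142 × 8) = 1.25 and exp(2 × 0.0221 × 8) = 1.42. The rule can therefore declare steady state while the interval includes a modelled rise of 25% or 42%.

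**Step 4: how often Days 3-11 passes.** 20,000 simulated trials per case, random-intercept model, independent residuals:

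| True profile | SD 0.16 | SD 0.25 | SD 0.35 |
|---|---|---|---|
| t½ 18 h (Day 3 at 84%) | 45% | 69% | 79% |
| t½ 15 h (Day 3 at 89%) | about 70% | 81% | 85% |
| Already flat | 90% | 90% | 90% |

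The pass rate rises with the noise. At SD 0.25 and 15 h it is within 10 percentage points of the rate for data truly at plateau.

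At lower noise the problem is smaller but remains. The shell's only row without ritonavir has a half-width of 0.012, so SD = 0.012 / 1.678 × √360 = 0.136 if n = 6. There the rule passes roughly one third of trials at 18 h and 62% at 15 h.

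**The case against.** The strongest reply is that this is a descriptive analysis with no hypothesis test, that Table 5.18 shows every slope with its interval, and that trough plots are also planned. A reader can see the estimates. That lowers the stakes but does not remove the fault, because the text still prescribes a yes/no conclusion, and it does so in a SAP whose stated approach is estimation.

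Several limits on the point do stand:

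- A reader might infer that troughs well below plateau will often be called steady state. The documents do not support this. At their unboosted half-life the lowest trough in the final window is 84 to 89% of plateau. A Day 3 trough of 75% would need a half-life of about 24 h, and a 25% rise over Days 6-11 does not fit 15 to 18 h either.
- A reader might infer that the Day 11 exposure or the accumulation ratios are unsafe. They are not: Day 11 is at plateau, and the ratios are simply Day 11 over Day 1, not conditional on this declaration.
- It is tempting to add that a precise but trivial slope would be declared not at steady state. The Protocol and SAP 2.4 wording allows that, but the near-zero alternative in SAP 9.2.5 is there to cover it. The defect in SAP 9.2.5 is that the alternative has no threshold.
- The shell values are examples from other regimens, with no sample size shown. They serve here only to suggest a noise level.
- The SD of 0.35 comes from Part 1 AUC and Cmax and is not a trough SD, so the 79 to 85% rates should carry little weight.

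**Conclusion.** The point holds in a moderate form. The rule takes a non-significant slope as proof of steady state, puts no limit on the remaining rise, and passes more readily as the data get noisier. From Day 3, when troughs are 84 to 89% of plateau, it declares steady state in about 45 to 70% of trials at SD 0.16 and 69 to 81% at SD 0.25.

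Troughs reach 94 to 96% of plateau on Day 4 and 98 to 99% on Day 5. The practical error is therefore a secondary endpoint set one or two days early.

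This rests on the assumed trough SD, one-compartment kinetics with linear accumulation, independent residuals, all 6 active participants with complete troughs, and the 15 to 18 h half-life carrying over to the Part 2 tablet dose. The rates are for the single Days 3-11 window; the selection of a time across successive windows was not simulated.

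**What to change.** In Protocol 10.4.2.3 and SAP 2.4 and 9.2.5, delete the sentence that declares steady state reached when the interval includes zero, and with it the undefined near-zero alternative in SAP 9.2.5. Replace it with, for example: 'For each window starting on Day k, the slope and the modelled change in trough from Day k to Day 11, exp[slope × (11 − k)], will be reported with 90% CIs. An interval that includes no change will be described as no trend detected, not as steady state reached.' Add the ratio and its interval to Table 5.18.

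The cost is a wording change and one derived result per window, with no new data or participants. The downside is that the report no longer gives a yes/no declaration.

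An equivalence margin is optional and is the sponsor's choice. With 6 participants, a rule that the 90% CI for this ratio must lie within 0.80 to 1.25 over Days 3-11 passes truly flat troughs 89%, 34% and 1% of the time at SD 0.16, 0.25 and 0.35. At 18 h and SD 0.16 it passes 40%, against 45% now. It reverses the reward for noise, but it is usable only if trough variability is low.

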10.4.2.4. Accumulation

For Part 2, the extent of accumulation of GSK2838232 will be evaluated by comparing AUC(0-τ), Cmax and Cτ between Day 11 and Day 1. For each of these comparisons an analysis of variance will be conducted on the log scale. The difference between Day 11 and Day 1 least square (LS) means and a 90% CI will be computed by fitting a mixed effects model with the log-transformed PK parameter as the dependent variable, day as a fixed effect and participant as a random effect. The estimated difference and confidence interval obtained on the log-scale will be exponentiated to provide an estimate of the Day 11 to Day 1 ratio and its associated 90% CI. If the model fails to converge, participants will be fit as a fixed effect.

10.4.3. Efficacy Analyses

Not applicable.

10.4.4. Other Analyses

Not applicable.

10.4.5. Interim Analyses

The dose and formulation to be administered in Part 1B and Part 2 will be decided, based on the outcome and results of an informal analysis of data from Part 1A of the study.

The Reporting and Analysis Plan will describe the planned interim analyses in greater detail.

12. APPENDICES

12.1. Appendix 1: Abbreviations and Trademarks

Abbreviations

AE	Adverse Event
AIDS	Acquired Immunodeficiency Syndrome
ALT	Alanine Aminotransferase
ANOVA	Analysis of Variance
API	Active Pharmaceutical Ingredient
ARV	Antiretroviral
AST	Aspartate Aminotransferase
AUC (0-t)	Area under the concentration-time curve from zero up to a definite time t
AUC(0-τ)	Area under the curve (Area under the plasma drug concentration- time curve from pre-dose to the end of the dosing interval at steady state)
AUC(0-inf)	Area under the concentration-time curve from time zero (pre-dose) extrapolated to infinite time
AV	Atrioventricular
BID	Twice Daily
BMI	Body Mass Index
BP	Blood Pressure
CFR	Code of Federal Regulations
CI	Confidence Interval
Cmax	Maximum observed concentration
Con Med	Concomitant medication
CONSORT	Consolidated Standards of Reporting Trials
CRF	Case Report Form
CRO	Contract Research Organization
CV	Cardiovascular
CYP	Cytochrome P subfamily of enzymes
DAIDS	Division of AIDS
DDI	Drug-drug Interaction
ECG	Electrocardiogram
ERCP	Endoscopic retrograde cholangio-pancreatography
FDA	Food and Drug Administration
FSH	Follicle Stimulating
FTiH	First Time in Human
GCSP	Global Clinical Safety and Pharmacovigilance
GSK	GlaxoSmithKline
HbsAg	Hepatitis B surface Antigen
hCG	Human Chorionic Gonadotrophin
HCV	Hepatitis C Virus
Hem/Chem	Hematology and Clinical Chemistry
HIV	Human Immunodeficiency Virus

HR	Heart Rate			
HRT	Hormone Replacement Therapy			
IB	Investigator's Brochure			
IEC	Independent Ethics Committees			
IRB	Institutional Review Board			
MedDRA	Medical Dictionary for Regulatory Activities			
MSDS	Material Safety Data Sheet			
NOAEL	No Adverse Event Dose Level			
PI	Principal Investigator			
PiB	Powder in Bottle			
PK	Pharmacokinetic(s)			
QD	Once daily			
RAP	Reporting and Analysis Plan			
RTV	Ritonavir			
SAE	Serious Adverse Event			
SOC	System Organ Class			
SOP	Standard Operating Procedure			
SRM	Study Reference Manual			
SSD	Spray Dried Dispersion			
SUSAR	Suspected Unexpected Serious Adverse Reactions			
t1/2	Apparent terminal phase half-life			
TEAE	Treatment-Emergent Adverse Event			
tlag	Lag-time (time delay between drug administration and first			
	observed			
tmax	Time of occurrence of Cmax			
ULN	Upper Limit of Norma			
US	United States (of America)			
WOCBP	Women of child bearing potential			
WPW	Wolf Parkinson White syndrome			

Trademark Information

Trade	emarks of the GlaxoSmithKline group of companies
NONE	

Trademarks not owned by the GlaxoSmithKline group of companies
Norvir
Phoenix
SAS
WinNonlin

